3.4. Stratification Factors

Cohorts 3 and 5, will be stratified by biopsy confirmed NASH with fibrosis status F1, F2 or F3 (Yes, No).

3.5. Sample Size and Power

No formal sample size calculation was performed for the primary endpoint(s) as the total of approximately 83 subjects, consisting of 6:2 (Cohort 1), 12:3 (Cohort 2), 9:3 (Cohorts 4 and 6) or 14:4 (Cohorts 3 and 5) receiving active: placebo, respectively is considered adequate to inform on the endpoints for this Phase 1b study.

A power assessment based on magnetic resonance imaging – proton density fat fraction (MRI-PDFF) endpoint (percent change from baseline to End of Treatment in liver fat content, an important biomarker) shows that 9, 12 and 14 subjects in a dose cohort compared to the pooled 19 placebo subjects will provide [REDACTED] power, respectively, to detect a difference in mean percentage change from baseline between treatment groups of [REDACTED], assuming

a standard deviation of █ in each group. Calculation was based on two-sample one-sided t-test with alpha at 0.05 (e.g., two-sided alpha at 0.10).

Subjects who withdraw from the study before the Day 50 assessments may be replaced at the discretion of the Sponsor.

3.6. Interim Analysis

No efficacy interim analysis is planned. Sponsor may perform administrative interim analyses to support objectives such as study planning and regulatory interactions.

3.7. Safety Monitoring Committee

A Safety Monitoring Committee (SMC), comprised of a Principal Investigator participating in the study, the Clinical Research Organization (CRO) Medical Monitor and the Sponsor Medical Monitor, will review blinded safety data for dose escalation decisions. The operations of the SMC will be defined in the SMC Charter.

4. Study Endpoints

4.1. Primary Endpoints

This study has primary safety and primary pharmacokinetic endpoints.

4.1.1. Safety Endpoints

The primary safety endpoints are:

- Subject incidence of treatment emergent adverse events (TEAEs)
- Subject incidence of TEAEs by severity
- Subject incidence of serious TEAEs
- Number of subjects who discontinued due to TEAEs
- Number of subjects who discontinued due to related TEAEs

4.1.2. Pharmacokinetic Endpoints

The primary pharmacokinetic endpoints are:

- Maximum concentration (C_{max}) on Day 1
- C_{max} on Day 29
- Area under the curve since last dose ($AUC_{0-\tau}$) on Day 1
- $AUC_{0-\tau}$ on Day 29
- Time to maximum concentration (t_{max}) on Day 1
- t_{max} on Day 29
- Half-life ($t_{1/2}$) on Day 1
- $t_{1/2}$ on Day 29

4.2. Secondary Endpoints

The secondary immunogenicity endpoints are:

- Incidence and characteristics of ADA after dosing (e.g., titer and/or binding specificity, to the fibroblast growth factor 21 (FGF21) and polyethylene glycol (PEG) part of BIO89-100 and neutralizing immunogenicity).
- Impact/correlation of the presence of ADAs on serum BIO89-100 concentrations and clinical safety.

The secondary pharmacodynamics endpoints are:

Anthropomorphic measurements:

- Change from baseline and percent change from baseline in body weight over time.
- Change from baseline and percent change from baseline in body mass index (BMI) over time.

Laboratory parameters:

- Change from baseline and percent change from baseline in triglycerides over time
- Change from baseline and percent change from baseline in non-high density lipoprotein (non-HDL) cholesterol over time
- Change from baseline and percent change from baseline in high density lipoprotein (HDL-c) over time
- Change from baseline and percent change from baseline in low density lipoprotein (LDL-c) over time
- Change from baseline and percent change from baseline in hemoglobin A1c (HbA1c) over time
- Change from baseline and percent change from baseline in homeostatic model of assessment of insulin resistance (HOMA-IR) over time

Liver function tests:

- Change from baseline and percent change from baseline in alanine transaminase (ALT) over time
- Change from baseline and percent change from baseline in aspartate transaminase (AST) over time
- Change from baseline and percent change from baseline in adiponectin over time
- Change from baseline and percent change from baseline in N-terminal propeptide of type III collagen (Pro-C3) over time
- Change from baseline and percent change from baseline in free fatty acids (FFA) over time
- Change from baseline and percent change from baseline in adipo-IR (fasting free fatty acids \times fasting insulin) over time

Imaging measures:

- Change from baseline and percent change from baseline in MRI-PDFF over time

[figure not shown]
- Percentage reduction from baseline in MRI-PDFF $\geq 30\%$ at Day 50 and Day 92
- MRI-PDFF $< 5\%$ at Day 50 and Day 92

4.3. Other Safety Endpoints

The other safety endpoints are:

- Change from baseline in vital signs
- Incidence and shifts of clinically significant vital signs
- Incidence of clinically significant physical examination findings
- Incidence and shifts of clinically significant electrocardiograms (ECG)
- Incidence and shifts of clinically significant laboratory abnormalities
- Change from baseline in safety laboratory evaluations including complete blood count (CBC), blood biochemistry, cortisol and urinalysis over time

4.4. Exploratory Endpoints

| Term | Percentage |
|------------|------------|
| GMOs | ~95% |
| Organic | ~95% |
| Natural | ~95% |
| Artificial | ~75% |
| Organic | ~95% |
| Natural | ~95% |
| Artificial | ~95% |
| Organic | ~95% |
| Natural | ~95% |
| Artificial | ~95% |
| Organic | ~95% |
| Natural | ~95% |
| Artificial | ~95% |

5. Definitions

5.1. Definition of Study Day

The day subjects receive their first dose of investigational product will be considered Study Day 1. Study day will be defined by the number of days from Study Day 1. If index date is prior to Study Day 1, study day will be defined as the index date minus the Study Day 1 date. If index date is on or after Study Day 1 date, the study day will be defined as index date minus the Study Day 1 date plus 1 day. If a subject is randomized but never dosed, study day will be calculated using the randomization date and randomization date will be set to Study Day 1.

For subjects with study interruptions due to COVID-19, post-interruption study day will be calculated as: (Index date) – (the date of Study Day 1) + 1 – (the interruption duration as defined in the study interruption CRF). Visits post-interruption due to COVID-19 will use this corrected study day for visit windowing.

5.2. Handling of Missing or Partial Dates

Date imputation will only be used for determining treatment-emergent status for adverse events or identifying concomitant medications. Actual data values as they appear in the database will be shown in the subject level listings.

5.2.1. Adverse Event Date Imputations

In cases of incomplete dates for adverse events, the missing components will be assumed as the most conservative values as possible. The imputation rules described below will attempt to conservatively capture AEs with missing onset dates as treatment-emergent, unless information

of AE stop date/time was prior to first dose date, which would automatically disqualify the treatment-emergent status. The original values with no imputation applied will be presented in the data listings.

- If “day” is the only missing field, impute the “day” as the day of Study Day 1 date if the month and year of Study Day 1 are equal to the AE start month and year; otherwise, impute the “day” as the first day of the AE start month.
- If “day” and “month” are missing, impute the “day” and “month” as the day and month of the first dose date if “year” is the same as the year of Study Day 1; otherwise, impute January 1 of the non-missing year.
- Missing time will not be imputed. If “time” is missing and the start date or imputed start date is the same as the first dose date, then the time is assumed to be after the dose time so that the event will be classified as treatment emergent.
- If the start date is completely missing:
 - and from the end date (either complete or partial date) it can be deduced to be prior to the first dose date, then the AE will not be assigned as a treatment-emergent adverse event (TEAE).
 - and from the end date (either complete or partial date) it cannot be deduced to be prior to the first dose date, then the AE will be assigned as a TEAE.
 - Start dates that are completely missing will not be imputed.

5.2.2. Medication/Procedure Date Imputations

Imputation of partial start and end dates for medications/procedures is done for the purpose of classifying concomitant, pre-treatment, and baseline medications/procedures. The original values with no imputation applied will be presented in the data listings.

For medications/procedures with completely missing start dates, no imputation will be performed.

For medications/procedures with partial start dates:

- If “day” is the only missing field, impute the “day” as the first of the month.
- If “day” and “month” are the missing fields, impute the “day” and “month” to January 1.
- If only day is missing, and month and year are the same as first dose date then consider as concomitant. For a medication/procedure that is not checked as ongoing and the start date is completely missing:
 - and from the end date (either complete, partial or completely missing) it can be deduced to be prior to the first dose date of randomized investigational product, then consider as pre-treatment.
 - Otherwise, consider as concomitant.

For medications/procedures with completely missing end dates and ongoing is not checked:

- End date will not be imputed, furthermore:

- If start date is on or after Study Day 1, then consider as concomitant medication/procedure
- If start date is prior to Study Day 1, or start date is also completely missing, then consider as pre-treatment medication/procedure
- If start date is on Study Day 1, then consider as baseline medication/procedure

For medications/procedures with partial end dates:

- If “day” is the only missing field, and if month and year are the same as the start date and ongoing is not checked, then impute “day” as the start date “day”; otherwise impute as the last day of the month.
- If “day” and “month” are the missing fields, if year is the same as the start date and ongoing is not checked, then impute “day” and month as the start date day and start date month; otherwise impute as December 31.

For medications/procedures that have both completely missing start dates and end dates, no imputation will be made; these medications/procedures will be assumed to be concomitant.

5.3. Definition of Study Baseline

For study measurements (safety labs, PD, biomarkers and exploratory labs) except ALT or AST, lipids, and vital signs, each subject’s baseline value for that measurement will be defined as the latest pre-dose value. This will be determined by chronologically sorting all scheduled and unscheduled values prior to first dose date and time and taking the latest value unless noted otherwise. Subjects who are randomized but are not dosed will use their latest measurement as baseline up to Study Day 1.

Baseline will be presented with each post-baseline change in the summary tables to allow easier review.

5.3.1. Study Baseline of ALT and AST

For ALT and AST, the baseline value will be defined as the average of all values performed during screening and Study Day 1 based on the following table. The baseline for ALT and AST are calculated and captured in the eCRF.

| ALT or AST Screening Assessments | | | Day 1 ALT or AST assessment | Baseline value |
|----------------------------------|---|--|--|---|
| Assessment 1 | Assessment 2 | Assessment 3 (if applicable) | | |
| Normal | Normal | Not applicable | Any | Average of Assessment 1, Assessment 2 and Day 1 (3 tests) |
| Normal | Abnormal and $\leq 40\%$ increase from Assessment 1 | Not applicable | Any | Average of Assessment 1, Assessment 2 and Day 1 (3 tests) |
| Normal | Abnormal and $>40\%$ increase from Assessment 1 | Normal or $\leq 40\%$ increase from Assessment 1 | Any | Average of Assessment 1, Assessment 2, Assessment 3 and Day 1 (4 tests) |
| Normal | Abnormal and $>40\%$ increase from Assessment 1 | Abnormal and $>40\%$ increase from Assessment 1 | Not applicable, subject excluded. | Not applicable, subject excluded. |
| Abnormal | $\leq 40\%$ increase from Assessment 1 | Not applicable | Any | Average of Assessment 1, Assessment 2 and Day 1 (3 tests) |
| Abnormal | $>40\%$ increase from Assessment 1 | $\leq 40\%$ increase from Assessment 1 | Any | Average of Assessment 1, Assessment 2, Assessment 3 and Day 1 (4 tests) |
| Abnormal | $>40\%$ increase from Assessment 1 | $>40\%$ increase from Assessment 1 | Not applicable, subject excluded. | Not applicable, subject excluded. |

5.3.2. Study Baseline for Lipids

For lipids, the baseline will be determined as the average of all pre-dose measurements within 30 days prior to Study Day 1, e.g. measurements taken at $-29 \leq \text{Study Day} \leq 1$ (Pre-dose).

5.3.3. Study Baseline for Vital Signs

For vital signs of blood pressure and pulse, measurements will be taken in duplicate starting from randomization. Baseline for these measures should be the last average (of the duplicate measurements) on or prior to Study Day 1 and prior to first dose if subject is dosed.

5.4. Definition of Duration of Exposure

The intended duration of exposure for QW dosing will be defined as the date of the last dose of investigational product minus Study Day 1 date plus 8 days. The intended duration of exposure for Q2W dosing will be defined as the date of the last dose of investigational product minus Study Day 1 date plus 15 days.

5.5. Definition of Age

Age will be defined as the duration in days of date of signed informed consent or index date minus the birthdate divided by 365.25. Index date refers to specific visits if age is needed at specific visits (for example age at specific visits will be used when deriving FIB-4 score or eGFR).

5.6. Dose Compliance

Dose compliance percentage will be the actual number of received doses divided by the expected number of doses to be received up to EOT. Partial doses will contribute to the actual number of received doses.

5.7. Definition of Pre-treatment Medication and Pre-treatment Procedures

Pre-treatment medications are defined as any medication that start and stop being taken prior to Study Day 1.

Pre-treatment procedures are defined as any procedure that were started and completed prior to Study Day 1.

5.8. Definition of Baseline Medication

Medications that have Study Day 1 within the duration of exposure will be considered baseline medications.

5.9. Definition of Concomitant Medication and Concomitant Procedures

Concomitant medications are defined as any medication that is taken any day on or after Study Day 1. This includes medications that were started prior first dose and that were continued to be taken after Study Day 1.

Concomitant procedures are defined as any procedures that are performed any day on or after Study Day 1. This includes procedures that were started prior first dose and that continued into Study Day 1.

5.10. Definition of Randomized Treatment Group

The definition of randomized treatment group, also known as the planned treatment group, will be the treatment group that a subject was randomized to. Placebo from each cohort will be pooled. The randomized treatment groups for summary purpose are: BIO89-100 3 mg QW, BIO89-100 9 mg QW, BIO89-100 18 mg QW, BIO89-100 27 mg QW, BIO89-100 18 mg Q2W, BIO89-100 36 mg Q2W, and Placebo.

[figure not shown]
5.11. Definition of Actual Treatment Group

The definition of actual treatment group will be the assigned treatment group based on what the subject actually received. If a subject receives at least one dose of BIO89-100, then that subject will be considered a subject of the active treatment group of the cohort that they were randomized to. If a subject receives only placebo doses, then their actual treatment group will be

placebo group. Placebo from each cohort will be pooled. The actual treatment groups for summary purpose are: BIO89-100 3 mg QW, BIO89-100 9 mg QW, BIO89-100 18 mg QW, BIO89-100 27 mg QW, BIO89-100 18 mg Q2W, BIO89-100 36 mg Q2W and Placebo.

5.12. Definition of Treatment Emergent Adverse Event

Treatment-emergent adverse events will be defined as those occurring at or after the time of the first administration of investigational product, eg, first dose date and time, through study termination, or existing prior to the time of and worsening after the time of the first administration of investigational product. Adverse events with onset prior to the first administration of investigational product that end before Study Day 1 or do not worsen after Study Day 1 will be classified as pre-treatment.

5.17. Adipo-IR

Adipo-IR will be calculated by multiplying fasting insulin (uU/mL) with the fasting free fatty acids (mmol/L) concentrations.

5.18. Estimated Glomerular Filtration Rate (CKD-EPI)

The eGFR using the CKD-EPI equation will be derived for post-baseline visits. Baseline eGFR will not be derived and will come from the source data.

For Males:

$$\begin{aligned}
 \text{eGFR[mL/min/1.73m}^2\text{]} \\
 = 141 \\
 * \min\left(\frac{\text{Serum Creatinine[mg/dL]}}{0.9}, 1\right)^{-0.411} \\
 * \max\left(\frac{\text{Serum Creatinine[mg/dL]}}{0.9}, 1\right)^{-1.209} * 0.993^{\text{Age[years]}} \\
 * 1.159[\text{if black}]
 \end{aligned}$$

For Females:

$$\begin{aligned}
 \text{eGFR[mL/min/1.73m}^2\text{]} \\
 = 141 \\
 * \min\left(\frac{\text{Serum Creatinine[mg/dL]}}{0.7}, 1\right)^{-0.329} \\
 * \max\left(\frac{\text{Serum Creatinine[mg/dL]}}{0.7}, 1\right)^{-1.209} * 0.993^{\text{Age[years]}} * 1.018 \\
 * 1.159[\text{if black}]
 \end{aligned}$$

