25. Any history of suicidal behavior or suicidal ideation with plan and intent based upon clinical history. A “yes” response to any of the suicidal ideation or suicidal behavior questions in the C-SSRS on Day -1.

26. Any clinically significant laboratory abnormality at screening. One repeat test may be allowed at the discretion of the Investigator. The presence of one or more of the following laboratory abnormalities should lead to exclusion of the subject from participating in the study:
 - a. ALT or AST ≥ 200 U/L
 - b. Elevation of total bilirubin (TB) $>$ ULN
 - c. Normalized ratio (INR) $>$ ULN
 - d. Alkaline phosphatase at screening $>1.25 \times$ ULN
 - e. Glomerular filtration rate (eGFR) ≤ 60 mL/min/1.73 m² as estimated by CKD-EPI Creatinine equation ([Levey, 2009](#))
 - f. Serum total triglycerides ≥ 1000 mg/dL
 - g. HbA1c $\geq 9.5\%$
27. ECG abnormality that may, in the opinion of the Investigator, interfere with study participation, including intraventricular conduction delays (QRS interval ≥ 120 msec or PR interval >200 msec (220 msec in individuals with a heart rate <70 beats per minute), and resting QTcF interval of ≤ 320 msec and/or ≥ 450 msec for males or ≥ 470 msec for females.
28. Vital sign abnormalities on screening, including: having a supine systolic blood pressure <90 or >150 mmHg, diastolic blood pressure (following at least a 5 minute rest) <50 or >95 mmHg, or resting heart rate <50 or >100 beats per minute.
29. BMI at screening <25 or ≥ 45 kg/m².

Other Exclusions

[figure not shown]
[figure not shown]
30. Known allergy or sensitivity to injected proteins, or any component of the formulation, or has a history of allergies (including food allergies) requiring acute or chronic treatment (except for seasonal allergic rhinitis).
31. Donated or received any blood or blood products (e.g., white blood cells, platelets) within the 60 days prior to screening, or has donated blood or blood products at least twice within the 6 months prior to screening, or the subject has donated plasma within 7 days of the screening visit, or has planned donations during the 56 days or 5 half-lives following the last day of study intervention administration, whichever is longer.
32. Any abnormality of the skin or abdominal wall that would affect SC administration to the abdominal area or any tattoos or scars in the intended injection area.

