9.1.1. Statistical Notation and Presentation

All data collected from all subjects in the electronic data capture will be presented in the subject level listings. All continuous data will be listed with the same precision as presented in the database. Data listings will be sorted by cohort, treatment group, subject ID and time point. Missing values will be represented by an empty cell and no imputation will be made. If imputation is used for analysis, excluding treatment-emergent and concomitant medication determinations, the imputed values will be listed with a derivation type column in the listing indicating that origin of the imputed value.

Continuous data will be summarized in tables using number of subjects or sample size (n), mean, median, standard deviation (SD), minimum and maximum. For logarithm-transformed data, the geometric mean, standard error (SE) of the geometric mean and geometric coefficient of variation (CV%) will also be provided.

Categorical data will be summarized in two ways, by subject and by time point. Subject data will be summarized using the count of distinct subjects that fall in the category and the percentage of the total number of subjects. Population counts, either the number of subjects or the number of assessments at the time point, will be used as the denominator in the calculation of percentages unless specified otherwise.

The original units (conventional) and SI units will be presented in listings. In general, conventional units will be used for tables and figures, unless otherwise specified. Insulin will use the conventional unit of uU/mL; estimated glomerular filtration rate will be presented using SI units.

Minimum and maximum values will use the precisions of the original value. Means, least squares (LS) means, and medians will be rounded to one decimal place greater than the precision of the original value up to a max of two decimal places. The limits of confidence intervals, standard deviations and standard errors will be rounded to two decimal places greater than the precision of the original value. Derived PK and PD data will be presented with three significant figures. Percentages will be rounded to the nearest tenth. Two-sided p-values will be presented with four decimal places and values less than 0.0001 will be presented as <.0001.

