9.5.2. Clinical Laboratory Evaluations

The observed values and the change from baseline for labs (biochemistry, hematology, urinalysis) will be summarized by visit and treatment group. Pharmacodynamic endpoints summarized via MMRM will not be presented in the safety lab change from baseline tables.

A listing of only abnormal labs (biochemistry, hematology, urinalysis) will be provided.

Shift tables will use the reference range result of low, normal, high to summarize lab (biochemistry and hematology) or normal and abnormal for select urinalysis shifts from baseline to each post-baseline visit. All labs with a reference range result will be included in shift tables. The percentage of the shifts will be derived using the number of subjects at the baseline range level as the denominator. Pharmacodynamic endpoints summarized via MMRM will be presented in the safety lab shift tables.

The observed value and the change from baseline in cortisol will be summarized descriptively in the urinalysis tables.

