5.13. Estimated Glomerular Filtration Rate (CKD-EPI)

The eGFR will be derived using the CKD-EPI equation.

For Males:

$$\begin{aligned}
 \text{eGFR}[\text{mL/min/1.73m}^2] &= 141 \\
 &\times \min \left(\frac{\text{Serum Creatinine}[\text{mg/dL}]}{0.9}, 1 \right)^{-0.411} \\
 &\times \max \left(\frac{\text{Serum Creatinine}[\text{mg/dL}]}{0.9}, 1 \right)^{-1.209} \times 0.993^{\text{Age}[years]} \\
 &\times 1.159[\text{if black}]
 \end{aligned}$$

For Females:

$$\begin{aligned}
 \text{eGFR}[\text{mL/min/1.73m}^2] &= 141 \\
 &\times \min \left(\frac{\text{Serum Creatinine}[\text{mg/dL}]}{0.7}, 1 \right)^{-0.329} \\
 &\times \max \left(\frac{\text{Serum Creatinine}[\text{mg/dL}]}{0.7}, 1 \right)^{-1.209} \times 0.993^{\text{Age}[years]} \times 1.018 \\
 &\times 1.159[\text{if black}]
 \end{aligned}$$

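### Part 1 eGFR: baseline is taken from source data but later visits are derived, so change from baseline mixes two calculations and carries a small avoidable artefact

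*SAP*

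**What the plan says.** Section 5.18 of the Part 1 SAP sets two rules for one variable. After baseline, "The eGFR using the CKD-EPI equation will be derived for post-baseline visits". For baseline, "Baseline eGFR will not be derived and will come from the source data". The section prints the equation, with a 1.159 multiplier for Black subjects, but says nothing about how the source value was computed. It requires no check that the two agree.

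Section 5.5 adds that "age at specific visits will be used when deriving FIB-4 score or eGFR", with age computed as days divided by 365.25, so the derived values use fractional age.

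The general rule in Section 5.3 is that a subject's "baseline value for that measurement will be defined as the latest pre-dose value". Its listed exceptions are ALT and AST, lipids, and vital signs; eGFR is not among them.

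On reporting, Section 9.5.2 states: "The observed values and the change from baseline for labs (biochemistry, hematology, urinalysis) will be summarized by visit and treatment group". Section 9.1.1 states that "estimated glomerular filtration rate will be presented using SI units". Section 4.3 lists change in blood biochemistry among the other safety endpoints.

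The Part 2 SAP, Section 5.13, makes no exception for baseline: "The eGFR will be derived using the CKD-EPI equation".

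**The concern.** A change score is interpretable only if both of its ends are measured the same way. Here one end is a reported number of unstated construction and the other is computed by the study's own formula. Any difference in age rule, rounding, race term or creatinine precision goes straight into the change, and the output would not separate it from a renal effect.

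What is at stake is the reading of a derived safety laboratory value: the within-group mean change, and any count of subjects crossing a threshold. The mismatch is also avoidable. Creatinine is a protocol chemistry test, and age, sex and race are collected, so nothing prevents deriving baseline as well.

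**Working it through.** The plan states no figure for eGFR or its change, so there is nothing to reproduce. The check holds creatinine fixed and asks what change the two-source rule would report.

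**Inputs**
- Equation, Part 1 SAP 5.18. Men: 141 × min(Cr/0.9, 1)^-0.411 × max(Cr/0.9, 1)^-1.209 × 0.993^age. Women: 0.7 replaces 0.9, -0.329 replaces -0.411, and the result is multiplied by 1.018. The factor 1.159 applies to Black subjects.
- Interval: Day 1 to Day 92 is 91 days, or 91/365.25 = 0.249 years.
- Grid: ages 21 to 75 (Part 1 inclusion), baseline eGFR above 60 (exclusion 26e), creatinine 0.50 to 1.44 mg/dL (chosen to span plausible values), both sexes, with and without the race factor.
- Source value: construction not stated. Exclusion 26e in Protocol 3.3.2 defines eGFR "as estimated by CKD-EPI Creatinine equation", and the central laboratory list in Appendix 12.3 of the Part 2 SAP includes a CKD-EPI GFR. Both suggest the same equation. The differences tested in steps 2 to 4 are assumptions.

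**Worked case: man, not Black, aged 55.5 at baseline, creatinine 0.9 mg/dL throughout.** Both creatinine terms equal 1.

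1. Both sides derived. Baseline: 141 × 0.993^55.5 = 141 × 0.67715 = 95.48. Day 92: 141 × 0.993^55.749 = 141 × 0.67596 = 95.31. Change: -0.17, which is ageing only.
2. Source uses whole-year age and integer rounding. Baseline: 141 × 0.993^55 = 95.81, reported as 96. Change: 95.31 - 96 = -0.69.
3. Source also rounds creatinine to one decimal. With a true creatinine of 0.94, Day 92 gives 141 × (0.94/0.9)^-1.209 × 0.67596 = 90.43. The source uses 0.9 and again reports 96. Change: -5.57.
4. The same man if Black, with a source value that omits the race factor. Day 92: 95.31 × 1.159 = 110.47. Change: 110.47 - 95.48 = +15.0.

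**Over the grid, creatinine unchanged (mL/min/1.73 m²)**

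| Baseline value | Smallest change | Largest change | Mean |
|---|---|---|---|
| Derived by the same formula | -0.31 | -0.10 | -0.17 |
| Source: whole-year age, integer rounding | -1.91 | +0.39 | -0.48 |
| Source: as above, plus creatinine to one decimal | -10.9 | +10.0 | -0.25 |

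A race-term mismatch depends on the level of eGFR. For a Black man aged 55 with creatinine 1.0, ignoring ageing, 141 × (1.0/0.9)^-1.209 × 0.993^55 = 84.4 without the factor and 84.4 × 1.159 = 97.8 with it, a difference of 13.4. For a Black woman aged 55.5 with creatinine 0.9, a source value of 71.7 becomes a derived 83.0 at Day 92, a change of +11.3. If the source applies the factor and the derivation does not, the signs reverse (-15.3 for the man in the worked case, -11.5 for this woman).

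**The case against.** The strongest reply is that little depends on this rule. Four parts of it stand.

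- **No named or primary analysis is touched.** The primary safety endpoints in Section 4.1.1 are incidences of treatment-emergent adverse events and discontinuations. A reader might infer that renal function belongs to the primary safety evaluation, but laboratory change sits in Section 4.3, and change in eGFR is implied by the general laboratory rules without being named.
- **Creatinine is analysed directly.** It is in Protocol Table 9, takes the latest pre-dose value as baseline, and gets its own change and shift tables. A reviewer who saw eGFR move while creatinine stayed still could recognise the artefact.
- **The source is probably the same equation.** A reader might take the 15.9% race-factor jump as the expected size. Nothing in the documents says the source omits the factor, and nothing says it includes it.
- **The source sample is not identified.** A reader might assume it is the screening value, up to 60 days before dosing. Section 5.18 does not say so, and a pre-dose laboratory sample is scheduled at the first dose.

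Nor do the documents support a claim of a uniform shift in every group. A rounding or age-rule difference would affect all groups alike and largely cancel against pooled placebo. A race-term difference would affect only Black subjects. False range shifts are likewise not established, because the Part 1 SAP does not say that a derived eGFR receives a low, normal or high flag.

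These points limit the size and importance. They do not make the two ends of the change score the same measure.

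**Conclusion.** The point holds, and it is minor. The Part 1 SAP prescribes two origins for one variable, so any tabulated change in eGFR contains a method difference. On the most likely reading (a CKD-EPI source differing only in whole-year age and integer rounding, which is an assumption), the artefact lies between about -1.9 and +0.4 mL/min/1.73 m². Shifts of 10 or more rest on assumptions the documents do not support: a source that treats race differently, or that uses coarser creatinine.

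The consequence is mainly for within-group change. Comparison with pooled placebo would be distorted only if a mismatch were unevenly spread. With 6 to 14 active subjects per cohort that could happen: under the race-term assumption, one affected subject would move a six-subject mean by 13.4/6 = 2.2. No primary endpoint, power figure or creatinine analysis is affected.

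**What to change.** In Part 1 SAP 5.18, replace the two sentences on derivation with a single rule: eGFR is derived by the equation shown at baseline, using the baseline creatinine defined in Section 5.3 and age at that visit, and at all post-baseline visits; the source eGFR is listed only.

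The cost is one sentence and one further derivation, with no new data, and it brings the rule into line with Part 2 SAP 5.13. If the SAP is already final, its introduction allows a justified deviation documented in the clinical study report. Using the laboratory-reported eGFR at every visit would be equally consistent, provided the laboratory reported it each time.
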